15.1.2.13 Section 9.2 Visit description**Old text:**

One month in the study schedule corresponds to 30 days. Although study visits should occur as close as possible to the time points specified in the protocol, a time frame of ± 7 days is allowed for Visit 2 (Month 1), and for the ~~unscheduled~~ Up-titration Visit(s). Starting from Visit 3 (Month 4), a time frame of ± 12 days is allowed for all regular visits.

[...]

New text:

One month in the study schedule corresponds to 30 days. Although study visits should occur as close as possible to the time points specified in the protocol, a time frame of ± 7 days is allowed for Visit 2 (Month 1), and for the Up-titration Visit(s). Starting from Visit 3 (Month 4), a time frame of ± 12 days is allowed for all regular visits.

All procedures and assessments should preferably be conducted **on the day of the visit**; however, if this is not possible for logistical reasons, the following time windows are allowed:

Blood sampling, ECG and recording of vital signs:

- Screening Visit and all visits starting from Visit 2: Visit date ± 7 days
- Run-In, PD and EOS Visit: Visit date ± 3 days

Sub-studies / iohexol and biomarker samples:

- all visits starting from Visit 3: Visit date ± 7 days
- PD and EOS Visit: Visit date ± 3 days

Sub-study / echocardiography (note that each time an echocardiography is performed, one blood sample should be drawn to assess the echo biomarkers):

- at Visit 1: Visit date -14 / +7 days
- Other visits: Visit date ± 30 days

[...]

15.1.2.14 Section 9.2.1 Run-in Visit (4 to 16 weeks prior to the Screening Visit)**Old text:**

- Take samples (hematology, HbA_{1c}, chemistry and urinalysis) for central laboratory evaluations (see Section 9.7.2.1).

New text:

- Take samples (hematology, HbA_{1c}, chemistry, urinalysis) for central laboratory evaluations (see Section 9.7.2.1)
Note: If HbA_{1c} cannot be analyzed by the central laboratory due to technical reasons,

subject can be considered suitable for randomization with one result only (Run-In or Screening).

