Discontinuation of study drug (for any reason) does not constitute the subject's withdrawal from the study, except if the investigator believes that it is in the best interest of the subject or if the subject withdraws consent (see Section 6.4.1 for details).

Details on procedures that are important to ensure the safety of the individual study subject are provided in the relevant sections of this protocol (i.e. *medical management, control of blood pressure and use of potassium supplements/lowering agents* in Section 8.1, and *monitoring blood potassium* in Section 9.7.1).

Follow-up Period

The period between the subject's last intake of study drug and last visit in the study is referred to as the '*Follow-up Period*'. If a subject withdraws from study drug permanently but does not withdraw from the study, this would apply to the period between the Premature Discontinuation (PD) Visit, which should take place as soon as possible following permanent discontinuation of study drug, and the EOS Visit. In the case where a subject discontinues treatment at the EOS Visit, the Follow-up Period applies to the period between the EOS visit and PT visit.

All subjects who had withdrawn consent can be followed up for vital status if they do not sign the '*Declaration of Objection*' form. In addition, vital status can be obtained by the investigator from publicly available data sources. The collection of vital status must be obtained within the timelines provided by Bayer.

End of study

The end of the study as a whole will be reached as soon as the last visit of the last subject of Study 16244 has been reached in all centers in all participating countries (EU and non-EU).

The study will terminate either when:

- (1) the targeted number of primary efficacy endpoint events have been positively adjudicated
- OR
- (2) at a recommendation of the DMC, whichever is earlier.

After notification of study termination, for all subjects still participating in the study, an End-of-Study (EOS) Visit should be scheduled as soon as possible (within 4 weeks of notification at the latest) to determine whether the subject had an event for inclusion in the primary or secondary endpoints.

Subjects who are still on treatment will discontinue study drug treatment at the EOS Visit and must perform the Post-Treatment (PT) Visit (4 weeks + 5 days) after their last dose of study drug.

The primary completion event for this study is the last visit for the last subject.

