Iohexol clearance ^b			X		X	X ^d	X ^d		X ^e	X ^e	X

NOTE:

One month corresponds to 30 days.

A time frame of ± 7 days is allowed for Visit 2 (Month 1).

A time frame of ± 12 days is allowed all regular visits from Visit 3 (Month 4) onwards.

Abbreviations: EOS = end of study; PD = premature discontinuation PK = Pharmacokinetics; PT = post-treatment; SD = study drug

^a Separate informed consent for each sub-study is required.

^b Sites in Italy only.

^c For all the subjects still on treatment with study drug at the EOS Visit, the PT Visit has to be performed 4 weeks + 5 days after last intake of study drug.

^d Every other visit (every 8 months) , i.e. Visit 5, Visit 7, Visit 9, Visit 11, etc.

^e Assessment at the end of the study, either at the PD Visit or the EOS Visit.

^f Time window for the assessment at Visit 1 is -14/+7 days, at other visits +/-30 days. Each time an echocardiography is performed, one blood sample should be drawn to assess the echo biomarkers

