9.2 Visit description - amended

This section was changed in Amendment 3, see Section 15.1.2.13.

One month in the study schedule corresponds to 30 days. Although study visits should occur as close as possible to the time points specified in the protocol, a time frame of ± 7 days is allowed for Visit 2 (Month 1), and for the Up-titration Visit(s). Starting from Visit 3 (Month 4), a time frame of ± 12 days is allowed for all regular visits.

All procedures and assessments should preferably be conducted on the day of the visit; however, if this is not possible for logistical reasons, the following time windows are allowed:

Blood sampling, ECG and recording of vital signs:

- Screening Visit and all the visits starting from Visit 2: Visit date ± 7 days
- Run-In, PD and EOS Visit: Visit date ± 3 days

Sub-studies / iohexol and biomarker samples:

- all visits starting from Visit 3: Visit date ± 7 days
- PD and EOS Visit: Visit date ± 3 days

Sub-study / echocardiography (note that each time an echocardiography is performed, one blood sample should be drawn to assess the echo biomarkers):

- at Visit 1: Visit date -14 / +7 days
- Other visits: Visit date ± 30 days

NOTE: If applicable, a subject who is not eligible at the Run-in or Screening Visit may be re-screened at a later time (see Section 6.4.2.1) or switch over to Study 17530 (see Section 6.4.2.2) provided the pre-requisites are met.

9.2.1 Run-in Visit (4 to 16 weeks prior to the Screening Visit) - amended

This section was changed in Amendment 3, see Section 15.1.2.14.

The following procedures and assessments will be performed at the Run-in Visit:

- Obtain signed informed consent (may be done earlier).
NOTE: any study-specific procedure can be performed only if written informed consent is **available**
- Check inclusion and exclusion criteria (see Sections 6.1 and 6.2)
- Collect demographic data, smoking status and alcohol consumption (see Section 9.3.1)
- Record medical history (see Section 9.3.2)
- Record use of prior and concomitant medication (see Section 8.1)
- Perform physical examination (see Section 9.7.3)
- Record body weight, height, waist and hip circumference (see Section 9.7.4)

- Record vital signs (see Section 9.7.5)
- Perform 12-lead ECG (see Section 9.7.6)
- Take samples (hematology, HbA_{1c}, chemistry and urinalysis) for central laboratory evaluations (see Section 9.7.2.1).

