- Take samples (potassium, creatinine) for local safety laboratory evaluations (see Section 9.7.2.2)
- Assess if the subject has any endpoint event(s) (see Table 13–1 and Section 9.6.1.3.1)
- Record adverse events (see Section 9.6.1), accounting for the rules of assessment and documentation (see Section 9.6.1.3).

9.2.9 Premature Discontinuation (PD) Visit (as soon as possible but within 7 days after study drug is permanently discontinued) - amended

The section title was changed in Amendment 3, see Section 15.1.2.21.

If the PD visit cannot be performed within the timeframe specified, no PD visit is required. The following procedures and assessments will be performed at the PD Visit:

- The subject completes KDQOL-36 and EQ-5D-5L questionnaires (see Section 9.7.7)
- Record use of concomitant medication (see Section 8.1)
- Collect unused study drug and perform accountability to assess compliance (see Section 7.6)

- Perform physical examination (see Section 9.7.3)
- Record body weight (see Section 9.7.4)
- Record vital signs (see Section 9.7.5)
- Perform 12-lead ECG (see Section 9.7.6)
- Take samples (hematology, HbA_{1c}, chemistry) for central laboratory evaluations (see Section 9.7.2.1)
- Optional: if the subject had signed informed consent for the sub-study, obtain respective samples for biomarkers (see Section 9.7.8.1.2) and/or for iohexol clearance (see Section 9.7.8.1.3), perform echocardiography (see Section 9.7.8.1.1)
- Assess if the subject has any endpoint event(s) (see Table 13–1 and Section 9.6.1.3.1)
- Record adverse events (see Section 9.6.1), accounting for the rules of assessment and documentation (see Section 9.6.1.3).

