9.7.8.1.3 Iohexol clearance sub-study - amended

This section was changed in Amendment 3, see Section [15.1.2.35](#).

At selected centers in Italy, at least 50 subjects per study consenting to participate in Studies 16244 and 17530 will be invited to take part in an iohexol clearance sub-study. Subjects will be asked to sign a separate informed consent to participate in this sub-study.

Subjects who are included in this sub-study will have their GFR directly measured by the iohexol plasma clearance technique (44).

Iohexol plasma clearance will be assessed at Visit 1 (Day 1, baseline), at Visit 3 (Month 4) and thereafter at every other visit (i.e. every 8 months) until the end of the study (either at the PD Visit or the EOS Visit) plus an additional assessment at the PT Visit (recovery). The Iohexol results will not be provided to the sites.

The variables for evaluation in this sub-study are as follows:

- Primary variable:
Chronic GFR slope, i.e. the rate of GFR decline from Visit 3 (Month 4) after randomization to the end of the treatment period.

As previously addressed in the AASK trial, this approach is needed to address the biphasic change in GFR decline that is expected after exposure to the study drug. The GFR slope will be determined separately during the first 4 months following randomization (acute slope) and after 4 months (chronic slope). The acute and chronic phases are differentiated because the study treatment might have acute effects on GFR that may differ from its long term effects on disease progression (45, 46) (an approach approved by the U.S. National Institute of Diabetes and Digestive and Kidney Diseases (47)).
- Exploratory variable:
 - Change in GFR from Visit 1 (baseline) and at the PT Visit (recovery)
 - Acute GFR changes from baseline to Visit 3 (Month 4)
 - Acute GFR changes from the end of the treatment period until the end of the recovery period
 - Correlation analyses between short term GFR changes between Visit 1 (baseline) and Visit 3 (Month 4) after randomization, and long term GFR decline (chronic slope).

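### The EOS and PD sub-study windows let the last iohexol GFR, biomarker sample and echocardiogram fall after study drug has stopped, so the chronic GFR slope can end on an off-drug value

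*Protocol*

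**What the plan says.** The operative windows are in Protocol Section 9.2; the Amendment 3 change log (Section 15.1.2.13) carries the same wording.

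- For iohexol and biomarker samples: "PD and EOS Visit: Visit date ± 3 days".
- For echocardiography after Visit 1, with the blood sample drawn alongside it: "Other visits: Visit date ± 30 days". Table 9-2 footnote f gives the same ±30 days and sets no separate limit for PD or EOS.
- The windows are a fallback for logistical reasons: "All procedures and assessments should preferably be conducted on the day of the visit".

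Two further rules fix where drug stops relative to these visits. Section 5 (End of study) states: "Subjects who are still on treatment will discontinue study drug treatment at the EOS Visit". The PD Visit (Section 9.2.9) is held "as soon as possible but within 7 days after study drug is permanently discontinued", and is not required if that limit cannot be met. Table 9-2 footnote e places the final sub-study measurement as follows: "Assessment at the end of the study, either at the PD Visit or the EOS Visit".

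Section 9.7.8.1.3 defines the primary iohexol variable as "Chronic GFR slope, i.e. the rate of GFR decline from Visit 3 (Month 4) after randomization to the end of the treatment period". One exploratory variable is "Acute GFR changes from the end of the treatment period until the end of the recovery period"; another compares baseline with the PT Visit. Under Table 9-2 footnote c, only subjects still on drug at EOS have a PT Visit, at 4 weeks + 5 days (days 28 to 33) after the last dose.

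**The concern.** The iohexol sub-study separates an acute from a chronic phase because it foresees that treatment may change GFR acutely, and it schedules a recovery test off drug. At Visit 1 the protocol protects drug status, since iohexol is measured before the first tablet. At the other end it does not: no text in the protocol or SAP requires the last measurement to precede the stop, or says how a later value is handled.

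If finerenone lowers GFR acutely and this reverses off drug, the reversal can occur only in the finerenone arm. A last value taken after the stop would then lift the end of the finerenone slope, in the direction that favours finerenone, in a sub-study planned with at least 50 subjects. For echocardiography and biomarkers (about 500 subjects each), time off drug could dilute the treatment difference at the last assessment.

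**Working it through.** The plan states no off-drug interval and no precision for the sub-study, so there is no figure of its own to reproduce.

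**1. Latest off-drug day.** This is the latest permitted visit day after the stop plus the latest permitted assessment day after the visit.

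| Route | Iohexol, biomarkers | Echocardiography |
|---|---|---|
| EOS (drug stops at the visit) | 0 + 3 = 3 days | 0 + 30 = 30 days |
| PD (visit up to 7 days after the stop) | 7 + 3 = 10 days | 7 + 30 = 37 days |

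An EOS echocardiogram on days 28 to 30 overlaps the PT window of days 28 to 33. The PD row is not a ceiling: if the PD Visit is missed, footnote e leaves the EOS Visit as the last assessment, possibly many months off drug.

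**2. Recovery variables.** Subjects on the PD route have no PT Visit, so the 10 days cannot enter. For the change from end of treatment to PT, the starting value is at most 3 days late: 3/33 = 9% to 3/28 = 11% of the interval, leaving 25 to 30 days. The baseline-to-PT change does not use the PD or EOS value.

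**3. Leverage on the slope.** I assume a least-squares slope per subject. The sub-study section does not name the fit; Section 10.3.3.5.2 uses per-patient linear regression for eGFR. With t in years, the weight of the last point is (t_last − mean t) / Σ(t − mean t)². Iohexol visits after Month 4 are every 8 months (Months 12, 20, 28), plus the final PD or EOS value. In months, the formula is multiplied by 12:

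- Months 4, 12, 20, 28, 30: mean 18.8, sum of squares 476.8, weight 12 × 11.2/476.8 = 0.282.
- Months 4, 12, 20, 24: mean 15, sum of squares 236, weight 12 × 9/236 = 0.458.
- Months 4, 12, 16: mean 10.67, sum of squares 74.67, weight 12 × 5.33/74.67 = 0.857.

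The slope shift is weight × reversal. The size of reversal is an assumption, shown for 0.5 to 3 mL/min/1.73 m²:

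| Last value at | Per 1 unit | 0.5 to 3 units |
|---|---|---|
| Month 30 (5 points) | +0.28/year | +0.14 to +0.85 |
| Month 24 (4 points) | +0.46/year | +0.23 to +1.37 |
| Month 16 (3 points) | +0.86/year | +0.43 to +2.57 |

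Early discontinuers have the shortest series, and so the largest weights.

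**4. Share affected by the PD route.** Section 10.4 plans 5% finerenone discontinuation per year. With an assumed mean follow-up of 11 + 33/2 = 27.5 months, 1 − 0.95^(27.5/12) = 11%, or 2.8 of an assumed 25 finerenone subjects. If all of them had an off-drug last value, each unit of reversal would move the arm mean by 0.111 × 0.282 = 0.03 to 0.111 × 0.857 = 0.10 per year. How many completers would be tested after the EOS Visit cannot be derived.

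**5. Analysis text.** SAP version 4.0 dropped the iohexol analyses because sub-studies are reported separately (SAP Section 7.3). Protocol Section 9.7.8.1.3 gives only an ANCOVA and correlations. The general efficacy rule in Protocol Section 10.1 counts values up to 30 days after the last dose as on treatment; if applied here, it would keep every value in the table of step 1 except an echocardiogram beyond day 30.

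**The case against.** The strongest reply has four parts.

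- Same-day testing is preferred, so the limits in step 1 are worst cases rather than typical practice, and the windows equally allow testing before the visit. This stands and limits the likely frequency.
- For discontinuers most of the gap comes from holding the PD Visit after the stop; the ±3 days adds at most 3. This also stands. Narrowing the window cannot cure the PD route, which needs a rule in the analysis.
- Handling may be set out in a separate sub-study plan or in the Echocardiography Manual, neither of which is available here. This is possible, but the Section 9.2 windows would still allow the late values.
- The SAP accepts values up to 30 days after last intake in its on-treatment eGFR analysis, and runs the post-Month 4 eGFR change to the PD or EOS Visit (SAP Section 6.2.3.3). That is a convention for the main trial. It does not answer a sub-study designed to separate acute effect and recovery from the chronic slope.

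A reader might go further and infer that the 10-day lag distorts the recovery estimate, or that late echocardiograms and biomarkers contaminate the GFR results. The documents do not support either. Discontinuers have no PT Visit, and neither echocardiography nor biomarkers enters a GFR variable. Those two are also described as end-of-study, not end-of-treatment, measurements.

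**Conclusion.** The point holds as a limited, cheaply avoidable weakness in the sub-studies. The permitted timing lets the chronic iohexol slope end up to 3 days (EOS) or 10 days (PD) off drug, and later after a missed PD Visit, although the variable is defined to the end of treatment. Per 1 mL/min/1.73 m² of reversal, an affected subject's slope rises by about 0.28 to 0.86 per year for series ending at Month 30 or Month 16, under a least-squares fit.

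The total bias cannot be stated. The documents say only that treatment might have acute effects on GFR. They give no size or speed of reversal and no share of subjects tested late. A reader might infer a definite bias of several tenths per year in the arm mean; that would rest on assumed inputs alone. The change from end of treatment to PT is exposed to at most 3 of 28 to 33 days, and the baseline-to-PT change is not exposed. For echocardiography and biomarkers the issue is possible dilution at the last assessment. The sub-studies are reported outside the main study report, and the trial's primary and secondary endpoints are unaffected.

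**What to change.** In Section 9.2 and Table 9-2, make the EOS sub-study windows one-sided for subjects still on drug at that visit: iohexol and biomarkers -3/0 days, echocardiography with its paired biomarkers -30/0 days. The test is then done no later than the EOS Visit. This moves only the measurement, not the time at which drug is stopped.

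In the sub-study analysis plan, record days since last dose for every last value, including EOS values after a missed PD Visit, and say whether such values enter the slope. Add a sensitivity analysis of the chronic slope that excludes off-drug values. Do not remove them from the main slope by a tight cut-off such as 1 day after the last dose: a subject stopping between Months 4 and 12 would keep only the Month 4 value and have no slope. Early discontinuers would thus be lost selectively, against the commitment in Section 11.4 to use their data as fully as possible.

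Cost: wording changes, earlier booking of some EOS tests within the existing 4 weeks from notification, and perhaps a few missed tests.

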15.1.2.15 Section 9.2.2 Screening Visit (≤ 2 weeks prior to Visit 1)

Old text:

- Take samples (hematology, HbA_{1c}, chemistry and urinalysis) for central laboratory evaluations (see Section 9.7.2.1).

New text:

- Take samples (hematology, HbA_{1c}, chemistry, urinalysis) for central laboratory evaluations (see Section 9.7.2.1)
Note: If HbA_{1c} cannot be analyzed by the central laboratory due to technical reasons, subject can be considered suitable for randomization with one result only (Run-In or Screening).

15.1.2.16 Section 9.2.3 Visit 1 (randomization; Day 1 and baseline)

Old text:

All measurements on Visit 1 are to be performed before first study drug intake. The following procedures and assessments will be performed at Visit 1:

[...]

- Optional: if the subject had signed informed consent for the sub-study, obtain respective samples for biomarkers (see Section 9.7.8.1.2) and/or iohexol clearance (see Section 9.7.8.1.3), perform echocardiography (see Section 9.7.8.1.1)

New text:

All measurements on Visit 1 are to be performed on the day of the visit before first study drug intake. The following procedures and assessments will be performed at Visit 1:

[...]

- Optional: if the subject had signed informed consent for the sub-study, obtain respective samples for biomarkers (see Section 9.7.8.1.2) and/or iohexol clearance (see Section 9.7.8.1.3), perform echocardiography (see Section 9.7.8.1.1)
Note: Time window for the echocardiography at Visit 1 is -14/+7 days. On the day the echocardiography is performed, a blood sample should also be drawn to assess the echo biomarkers.

15.1.2.17 Section 9.2.5 Visit 3 (Month 4)**Old text:**

- Obtain sample for PK (see Section 9.5)

New text:

- Obtain pre-dose sample for PK (see Section 9.5)

15.1.2.18 Section 9.2.6 Visit 4, 6, 7, 9, etc. (every 4 months; Month 8, 16, 20, 28, etc., excluding yearly visits)**Old text:**

- Take samples (potassium, creatinine) for local safety laboratory evaluations (see Section 9.7.2.2)
- Optional: if the subject had signed informed consent for the sub-study, obtain samples for iohexol clearance (see Section 9.7.8.1.3).
Note: Iohexol clearance should be performed every 8 months only

New text:

- Take samples (potassium, creatinine) for local safety laboratory evaluations (see Section 9.7.2.2)
- **Visit 4 only:** Obtain pre-dose sample for PK if no PK sample was taken at Visit 3 (see Section 9.5)
- Optional: if the subject had signed informed consent for the sub-study, obtain samples for iohexol clearance (see Section 9.7.8.1.3).
Note: Iohexol clearance should be performed every 8 months only (Visit 7, Visit 9, etc.)

15.1.2.19 Section 9.2.7 Visit 5, 8, 11, etc. (every 12 months; Month 12, 24, 36, etc.)**Added text:**

- Optional: if the subject had signed informed consent for the sub-study, obtain samples for iohexol clearance (see Section 9.7.8.1.3).
Note: Iohexol clearance should be performed every 8 months only (Visit 5, Visit 11, etc.)

15.1.2.20 Section 9.2.8 Up-titration Visit (unscheduled; from 4 weeks \pm 7 days post-titration)**Old text:****9.2.8 Up-titration Visit (unscheduled; from 4 weeks \pm 7 days post-titration)**

The following procedures and assessments will be performed at the Up-titration Visit. ~~These procedures also apply for a re-start of study drug after interruption of study drug intake.~~

- Record use of concomitant medication (see Section 8.1)
- Collect unused study drug and perform accountability to assess compliance (see Section 7.6)

New text:**9.2.8 Up-titration Visit (4 weeks \pm 7 days after up-titration or restart of study drug, and for up-titration of study drug)**

The following procedures and assessments will be performed at the Up-titration Visit (see Section 7.4 for details).

- Record use of concomitant medication (see Section 8.1)
- Collect unused study drug and perform accountability to assess compliance, if applicable (see Section 7.6)

15.1.2.21 Section 9.2.9 Premature Discontinuation (PD) Visit**Old text:****9.2.9 Premature Discontinuation (PD) Visit**

The following procedures and assessments will be performed at the PD Visit:

New text:**9.2.9 Premature Discontinuation (PD) Visit (as soon as possible but within 7 days after study drug is permanently discontinued)**

If the PD visit cannot be performed within the timeframe specified, no PD visit is required.

The following procedures and assessments will be performed at the PD Visit:

